7. For candidemia only subjects, drawing of a set of blood cultures within 12 hours prior to randomization in the study. The result of these blood cultures is not required for inclusion in the study.

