An insufficient therapeutic effect may be determined prior to the planned duration of therapy in the study. This determination will require an assessment of clinical status including the synthesis of symptoms and signs data (both local and systemic). Subjects who are deemed to have an insufficient therapeutic effect should be discontinued from study drug therapy.

If a subject has daily blood cultures positive for *Candida* spp. through Day 7 despite appropriate study drug administration, this should be considered an insufficient therapeutic effect and study drug should be discontinued and salvage therapy initiated. The subject should remain in the study through the Follow-up visit (Days 52–59) to complete safety assessments and assess for mortality.

Seven days is the maximum number of daily positive blood cultures allowed prior to a change in antifungal therapy. The Investigator may determine that there is an insufficient therapeutic response prior to Day 7.

- Investigator discretion
 - Resistant Pathogen(s): In the event an organism resistant to ≥ 1 of the potential study drugs is isolated, the Investigator will determine whether the subject remains on study drug therapy. The Investigator may decide to continue study drug therapy if, in the Investigator's opinion, there is clear and continuing clinical improvement while on therapy.
 - The Investigator may decide to prematurely discontinue study drug therapy and to initiate an alternative and appropriate therapy if, in the Investigator's opinion, the subject is not benefiting from study drug.

NOTE: The Medical Monitor should be contacted to discuss whether to continue or prematurely discontinue a subject on the study drug in the event the subject requires systemic concomitant antifungal therapy.

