Failure	
 • If positive blood culture at baseline: 
 ○ The last blood culture drawn on or prior to the day of assessment is positive for Candida spp. from a sample drawn following the first dose of study drug, OR • If positive culture from a normally sterile site at baseline: 
 ○ Documented mycological persistence: most recent culture on or prior to the day of assessment from all normally sterile sites of baseline Candida infection (if accessible) is positive and culture was obtained after the initiation of study drug, OR ○ Presumed mycological persistence: follow-up culture from all normally sterile sites of baseline Candida infection is not available (e.g., normally sterile baseline site of Candida infection not accessible) OR the most recent culture from all normally sterile sites of baseline Candida infection obtained after initiation of study drug is positive in a subject without a successful clinical outcome as assessed by the Investigator or without a successful radiological outcome for those with documented evidence of disease from imaging at baseline, OR • The subject requires a change of antifungal therapy to treat candidemia and/or invasive candidiasis, OR • The subject dies of any cause prior to or on the day of assessment.
Indeterminate	
Study data are not available for the evaluation of efficacy for any reason including:
 
 • If positive blood culture at baseline: A post-baseline blood specimen was not available to culture or the result was not available. • If positive culture from a normally sterile site at baseline: A sterile site/fluid post-baseline specimen was not available to culture or the result was not available AND an assessment clinical outcome by the Investigator was not available or radiographic assessments are not available. • Subject is lost to follow-up on the day of assessment.

* Presumed eradication is defined only for a culture from a normally sterile site and is not defined for a blood culture.

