Failure	
 • If positive blood culture at baseline: 
 ○ The last blood culture drawn on or prior to the day of assessment is positive for Candida spp from a sample drawn following the first dose of study drug, OR • If positive culture from a normally sterile site at baseline: 
 ○ Documented mycological persistence: culture on the day of assessment from all normally sterile sites of baseline Candida infection (if accessible) is positive, OR ○ Presumed mycological persistence: follow-up culture from all normally sterile sites of baseline Candida infection is not available (eg, normally sterile baseline site of Candida infection not accessible) OR the most recent culture from all normally sterile sites of baseline Candida infection obtained after initiation of study drug is positive, in a subject without a successful clinical outcome as assessed by the Investigator or without a successful radiological outcome for those with documented evidence of disease from imaging at baseline, OR • The subject requires a change of antifungal therapy to treat candidemia and/or invasive candidiasis***, OR • The subject dies of any cause prior to or on the day of assessment.
Indeterminate	
Study data are not available for the evaluation of efficacy for any reason including:
 
 • If positive blood culture at baseline: A post-baseline blood specimen was not available to culture or the result was not available. • If positive culture from a normally sterile site at baseline: A sterile site/fluid post-baseline specimen was not available to culture or the result was not available AND an assessment clinical response by the Investigator was not available or radiographic assessments are not available. • Subject is lost to follow-up on the day of assessment.

* Presumed eradication is defined only for a culture from a normally sterile site and is not defined for a blood culture.

**Table includes clarifications that are not in the protocol.

*** Defined as receipt of an antifungal with an indication of Candidemia/invasive candidiasis, *Candida* endophthalmitis/chorioretinitis or *Candida* endocarditis which started on or prior to the day of assessment or started on EOT (+ 1 day).

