Documented evidence of IC at baseline is defined as having a radiologic test prior to the first dose of study drug that indicates new radiologic evidence of IC. Subjects who are diagnosed with IC by tissue/fluid culture whose first radiologic test is after the first dose of study drug are considered not to have a baseline radiologic test. In these subjects, radiology is not used to determine response.

Subjects who are diagnosed with candidemia at baseline (ie, prior to initiation of study drug) and progress to IC based on radiographic evidence or a tissue/fluid culture are considered to have IC for subsequent outcome assessments. The radiograph or tissue/fluid culture used to document progression is considered the baseline radiograph or tissue/fluid culture for outcome assessment.

The mycological eradication rate is the proportion of subjects with success (eradication/presumed eradication) out of the total number of subjects in the specified analysis population.

2.2.3. **Investigator's Assessment of Clinical Response**

The Investigator will make a determination of clinical cure at Day 5, Day 14 (± 1 day), Day 30 (-2 days), End of Treatment (≤ 2 days of last dose), and Follow Up (Days 52-59) according to the definitions in **Table 2-4**.

Subjects whose disease is progressing or who receive rescue antifungal therapy for candidemia/IC prior to an assessment time point will be considered a clinical failure at the assessment time point and all subsequent time points. Subjects who do not have resolution of systemic signs and symptoms but are improving at the day of assessment are considered a clinical failure. As long as no rescue antifungal therapy for candidemia/IC was received, the subject may still qualify as a cure at future visits as long as they meet the criteria of clinical cure at those visits. For example, at Day 14 (± 1 day) and Day 30 (-2 days), a subject who is on study drug can be a clinical cure if no rescue antifungal therapy for candidemia/IC was received and the subject meets the criteria of clinical cure even if they were assessed as a clinical failure at the Day 5 visit.

Table 2-4: Investigator’s Assessment of Clinical Response Definitions

Clinical Response	Definition

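### Apart from antifungal change and death, mycological failure is judged only at baseline-positive sites, so new unresolved Candida elsewhere can be programmed as Eradication

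*SAP*

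**What the plan says.** Mycological response is derived by program from the eCRF and mycology data at Day 5, Day 14, Day 30, End of Treatment and Follow-up (SAP 2.2.2). The rules are in SAP Table 2-3 and, with the same structure, in protocol Table 8 (Section 10.2.1).

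- **Blood.** The blood limbs of both the Eradication and the Failure rows open with "If positive blood culture at baseline". Without positive blood at baseline, no post-dose blood result is consulted.
- **Sterile sites.** Documented persistence in the SAP is a positive "culture on the day of assessment from all normally sterile sites of baseline" Candida infection. The protocol has "most recent culture on or prior to the day of assessment from all normally sterile sites of baseline" Candida infection. The two differ on timing, but both look only at baseline sites. The eradication and presumed limbs carry the same restriction.
- **Criteria not tied to a site.** There are two: "The subject requires a change of antifungal therapy to treat candidemia and/or invasive candidiasis" and "The subject dies of any cause prior to or on the day of assessment".
- **Progression.** The text after SAP Table 2-3 covers "Subjects who are diagnosed with candidemia at baseline (ie, prior to initiation of study drug) and progress to IC". For them, the culture or image that shows progression becomes the new baseline. Nothing covers a subject with invasive candidiasis (IC) who develops candidemia or a new infected site.

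Global response (SAP Table 2-2) combines mycological, clinical and, where imaging showed disease at baseline, radiological response. The DRC's determination is the one analysed.

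**The concern.** A subject enrolled on a sterile-site culture alone is never judged on blood, and never on a site that was not infected at baseline. If Candida appears in either place on treatment and is still there at the assessment, no culture-based failure limb applies. If the baseline site has cleared, every Eradication condition is met.

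An endpoint named eradication should not be met by a subject whose latest blood culture grows Candida. The population is not remote. The blood culture shortly before randomization is an inclusion requirement only for some subjects ("For candidemia only subjects, drawing of a set of blood cultures within 12 hours prior to randomization in the study"), so an IC subject's candidemia may first be seen after dosing.

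At stake are a secondary endpoint reported at five visits and, by a narrower route, one component of the EMA primary endpoint. Every affected subject has IC, which is a reported subgroup for secondary outcomes and a formal superiority step for global cure (SAP 4.3.1 and 4.3.2).

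**Working it through.** **1. Apply the tables.** Take a subject with a positive sterile-site culture and no positive blood at baseline. The baseline site is now documented negative, and the subject is alive and not lost to follow-up. The latest blood culture, or a culture from a new sterile site, is positive. Tables 2-3 and 2-2 then give:

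| Antifungal changed | Clinical response | Mycological | Global, before DRC review |
|---|---|---|---|
| No | Cure | Eradication | Cure (radiology permitting) |
| No | Failure | Eradication | Failure |
| Yes | Either | Failure | Failure |

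If the baseline site is not documented negative, presumed eradication gives the first row's result, because it requires clinical success. An IC subject whose blood was positive at baseline, and whose last blood culture is positive, is a Failure on both scales in every case.

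So the mycological result is wrong in the first two rows, and the global result is open to error only in the first. If an unresolved new positive culture counted as failure, both rows would become mycological Failure and the first would become global Failure. Nothing else in the table would change.

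**2. Denominator.** The plan requires 92 per arm in the mITT population. Inputs (Protocol 13.8, SAP 3.1): cure 70% in both arms, margin 20%, one-sided alpha 0.025, power 80%.

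- Uncorrected: n = 2 × 0.7 × 0.3 × (1.960 + 0.842)² / 0.20² = 82.4.
- Continuity corrected: (82.4/4) × [1 + √(1 + 4/(82.4 × 0.20))]² = 92.1.

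This agrees with 92, which serves here only as the denominator.

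**3. Size per subject.** 1/92 = 1.09 percentage points of an arm's rate.

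**4. Illustration only.** The documents give no rate for this event. Assume the Phase 2 IC share of 20.8% at study entry (Protocol 4.7.2), so 0.208 × 92 = 19.1 IC subjects per arm. Assume also that 2%, 5% or 10% of them show the pattern.

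| Assumed rate | Subjects per arm | Points of the arm's rate |
|---|---|---|
| 2% | 0.4 | 0.4 |
| 5% | 1.0 | 1.0 |
| 10% | 1.9 | 2.1 |

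For a given rate these are upper limits if every IC subject is counted as at risk. Subjects positive in both blood and a sterile site are randomized in the IC stratum (Protocol 6.5) and are already judged on blood. Those who change antifungal or die already fail. Within the IC subgroup, one subject is 1/19, about 5 points.

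**5. Against the margin.** With equal observed cure rates of 70%, the approximate 95% half-width is 1.96 × √(2 × 0.7 × 0.3/92) = 13.2 points, so the lower limit is near −13. Put the whole 10% case in the rezafungin arm (67.9% against 70%). The half-width becomes 1.96 × √[(0.679 × 0.321 + 0.7 × 0.3)/92] = 13.4, and the lower limit is −2.1 − 13.4 = −15.5, still inside −20.

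**The case against.** The strongest case against the point concerns the primary endpoint. A reader might infer that the plan will count new candidemia as global cure. The documents do not support that:

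- The analysed response is the blinded DRC's. The clinically evaluable definition in SAP 2.6 speaks of mycological and clinical response as assessed by the DRC, so the committee judges mycology itself. Its charter is not among the documents.
- Global cure needs clinical cure, which new attributable signs or a new systemic antifungal defeat. SAP 2.2.3 makes progressing disease a clinical failure at that visit and all later ones.
- Antifungal change or death is failure whatever the site.

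A reader might also take the Protocol 7.4.2 statement "Seven days is the maximum number of daily positive blood cultures allowed prior to a change in antifungal therapy" as permission for breakthrough candidemia. In context it is a limit that ends in stopping study drug and starting salvage therapy, which Table 2-3 scores as failure.

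Nor does it matter that candidemia is first found just after dosing if it then clears. A rule based on the most recent culture would also call that eradication.

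All of this narrows the route to global cure without closing it. Table 2-4 describes progression through signs and symptoms and names no culture. Radiology is set aside for IC subjects without pre-dose imaging. None of it repairs the programmed endpoint, which neither the investigator nor the DRC can override. At Day 5 the seven-day limit has not been reached, and the SAP footnote counts an antifungal change only if it started by the assessment day (with an allowance at End of Treatment). A later change would therefore not correct the Day 5 score.

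**Conclusion.** The gap is real in both documents for the programmed mycological eradication endpoint, at all five visits. A subject enrolled on a sterile-site culture, without positive blood at baseline, is scored as Eradication despite new unresolved Candida in blood or at a new sterile site. The conditions are that the baseline site is cleared or presumed cleared, therapy is unchanged and the subject is alive. For global cure the route is narrow and depends on clinical cure, radiological cure where it applies, and DRC acceptance.

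No firm size can be stated. Each affected subject is worth about 1.1 points of an arm's rate, and the rates in the illustration are assumed. The overall conclusion against the 20% margin is unlikely to change, and no sample size, power or alpha figure is affected.

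A reader might infer a bias toward non-inferiority. The documents do not show one. Misclassification at similar rates under blinding leaves the difference nearly unchanged, and nothing suggests that the arms differ in this event.

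**What to change.** Before unblinding:

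1. In SAP Table 2-3 and protocol Table 8, add a Failure criterion for all subjects. It applies when the most recent post-dose blood culture, or the most recent post-dose culture from a normally sterile site that was not a baseline site, on or before the assessment day, is positive for Candida. Make its absence a condition of Eradication. Keep *most recent* for both parts, so that a cleared infection does not count as failure.
2. Extend the progression rule in SAP 2.2.2 to IC subjects who develop candidemia or a new site. State that criterion 1 takes precedence while the latest culture there is positive.
3. Leave the presumed-eradication limb for baseline sites as it is, since it deliberately accepts a positive last culture with clinical and radiological success. State how to classify a subject with one cleared and one still-positive baseline site. As written, neither *all negative* nor *all positive* is true of that subject. Align the timing wording of documented persistence between the two documents in the same edit.
4. Tell the DRC of the same rule.

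The cost is wording in two tables and one paragraph, a change to the derivation program and a note to the DRC. It uses culture results already collected. The downside is that the reported eradication rate may be slightly lower.

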7.2 Subject Exclusion Criteria

Subjects must NOT meet any of the following exclusion criteria to qualify for the study:

1. Any of the following forms of invasive candidiasis at baseline:
 - a. Septic arthritis in a prosthetic joint (septic arthritis in a native joint is allowed)
 - b. Osteomyelitis
 - c. Endocarditis or myocarditis
 - d. Meningitis, endophthalmitis, chorioretinitis, or any central nervous system infection
 - e. Chronic disseminated candidiasis
 - f. Urinary tract candidiasis due to ascending *Candida* infection secondary to obstruction or surgical instrumentation of the urinary tract
2. Received systemic treatment with an antifungal agent at approved doses for treatment of candidemia for > 48 hours (e.g., > 2 doses of a once daily antifungal agent or > 4 doses of a twice daily antifungal agent) ≤ 4 days (96 hours) before randomization.
 - a. Exception: Receipt of antifungal therapy to which any *Candida* spp. isolated in culture is not susceptible (see [Appendix 1](#))
3. Alanine aminotransferase or aspartate aminotransferase levels > 10 -fold the upper limit of normal (ULN).
4. Severe hepatic impairment in subjects with a history of chronic cirrhosis (Child-Pugh score > 9).

5. Presence of an indwelling vascular catheter or device that cannot be removed or an abscess that cannot be drained and is likely to be the source of candidemia or invasive candidiasis.
6. Known hypersensitivity to Rezafungin for Injection, caspofungin, any echinocandin, or to any of their excipients, including but not limited to hereditary sugar disorders (e.g., fructose intolerance, sucrose-isomaltase insufficiency), anaphylaxis, or echinocandin-induced exfoliative skin disorders (e.g., Stevens-Johnson syndrome or toxic epidermal necrolysis).
7. Meets National Cancer Institute Common Terminology Criteria for Adverse Events (CTCAE) version 5.0, criteria for ataxia, tremor, motor neuropathy, or sensory neuropathy of Grade 2 or higher.
8. History of severe ataxia, tremor, or neuropathy or a diagnosis of multiple sclerosis or a movement disorder (including Parkinson's Disease or Huntington's Disease).
9. Planned or ongoing therapy at Screening with a known severe neurotoxic medication (see [Appendix 9](#)) or with a known moderate neurotoxic medication (see [Appendix 9](#)) in a patient with ataxia, tremor, motor neuropathy, or sensory neuropathy of CTCAE version 5.0 Grade 1 or higher.
10. Previous participation in this or any previous rezafungin study.

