2.3.3. Time to First Negative Blood Culture

Time to first negative blood culture is defined in hours from the first dose of study drug to the first negative blood culture without subsequent positive cultures following the first pre-treatment blood culture confirmed positive for any *Candida* species. Blood culture results from both location 1 and location 2 need to be negative if the samples were taken from 2 locations on the same day. Subjects will be censored at the earliest start date and time of receipt of a new antifungal (i.e., other than study drug) for the treatment of candidemia received any time on/after the date and time of the first dose of study drug if it was used prior to having a negative blood culture. If a subject is lost to follow-up or died prior to having a negative blood culture, the subject will be censored at the date of the last blood culture. The details about the censoring rules under different scenarios are shown in the following table:

Blood Culture Result	Antifungal Use	Event (Negative Culture) or Censor	Event or Censoring Date
Negative blood culture without subsequent positive cultures	Not used or used after negative blood culture	Event	Earliest blood culture date with negative result
Negative blood culture obtained prior to first dose date and no subsequent positive cultures	Not used or used after negative blood culture	Censor	First dose date
No negative blood culture	Not used	Censor	Last blood culture date
No negative blood culture	Used	Censor	Earlier date between the last blood culture date and the antifungal start date

The number and percentage of subjects with a negative blood culture at 24 and 48 hours post first dose will also be provided by treatment group. The denominator will include subjects who were either not censored in the time to negative blood culture analysis or who were censored after 24 or 48 hours, respectively.

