positive culture at randomization definition 1 (defined in Section 2.8), 2) Subjects who did not receive systemic antifungal therapy prior to the first dose of study drug, 3) Subjects diagnosed with Candidemia only, and 4) Subjects diagnosed with Candidemia only with timing of positive culture at randomization definition 1 (defined in Section 2.8).

Results of blood culture, tissue/fluid culture from a normally sterile site, rapid diagnostic and radiological (and other imaging) testing will be provided in by-subject listings.

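### The SAP's derived-failure rule for a change of antifungal therapy has no first-dose limit and no study-drug exclusion, so as written it fails subjects who had permitted pre-study treatment

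*SAP*

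**What the plan says.** SAP 2.2.2 has mycological response determined by program from eCRF and mycology data, using Table 2-3. The failure criteria there are alternatives, so meeting one is enough. One of them is: "The subject requires a change of antifungal therapy to treat candidemia and/or invasive candidiasis". The triple-asterisk footnote gives this criterion its operational meaning: "Defined as receipt of an antifungal with an indication of Candidemia/invasive candidiasis", or of Candida eye infection or endocarditis, "which started on or prior to the day of assessment", with a further clause for a start at EOT (+1 day).

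Protocol 7.2, Exclusion 2, reads: "Received systemic treatment with an antifungal agent at approved doses for treatment of candidemia for > 48 hours", within the four days before randomization, with an exception when an isolate is not susceptible to the drug given. Treatment for 48 hours or less is therefore allowed. Protocol 8.5 has systemic antifungals from the four weeks before randomization entered in the eCRF.

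Elsewhere the SAP does separate the two periods. For time to first negative blood culture, SAP 2.3.3 censors only at a new antifungal, other than study drug, "received any time on/after the date and time of the first dose of study drug". SAP 4.2.2 tabulates antifungals taken before the first dose apart from later ones, and leaves study drug out of the later group. SAP 4.3.4 plans a repeat of the blood-culture analysis in this subset: "Subjects who did not receive systemic antifungal therapy prior to the first dose of study drug". Pre-study treatment is thus expected in the mITT population.

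**The concern.** The footnote fixes the latest start date that counts but not the earliest. A drug given for candidemia before randomization has a listed indication and began before every assessment day, so it satisfies the rule at all five visits. Permitted prior treatment would then be classified as if it were rescue.

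The endpoint at stake is derived mycological eradication, a secondary outcome at Day 5, Day 14, Day 30, EOT and Follow-up (SAP 2.2 and 4.3.2). The same derived value enters the Day 14 outcomes by baseline species and MIC (SAP 2.3.4) and the analysis of sign resolution among subjects who also have eradication (SAP 4.3.4). Forcing the same share of both arms to failure lowers both rates and narrows any real difference between them. A chance imbalance in prior treatment would appear as a treatment difference.

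**Working it through.** **The plan's own figures.** The plan states no expected eradication rate, so there is none to reproduce. Its sample size does reproduce. With 70% global cure in both arms, a 20% margin, one-sided alpha 0.025 and 80% power, the uncorrected size is n0 = 0.42 × (1.960 + 0.842)² / 0.20² = 82.4 per arm. The continuity correction (n0/4) × (1 + √(1 + 4/(n0 × 0.20)))² gives 92.1 per arm, against 92 stated (184 in total). The point below does not depend on these figures.

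**Step 1: apply the footnote to a permitted case.** Take a subject given one day of an antifungal for candidemia before randomization, whose cultures are negative from Day 2 onward.

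| Condition in the footnote | Met? |
|---|---|
| An antifungal was received | Yes, and it is recorded (Protocol 8.5) |
| The indication is on the list | Yes, if entered as candidemia or invasive candidiasis |
| It began no later than the assessment day | Yes, at every visit |
| It began after the first study-drug dose | Not asked |
| It is not study drug | Not asked |

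The subject meets a failure criterion at every visit, regardless of cultures. The Eradication row requires that there was no such change, so if the term means the same there, the subject cannot qualify in that row either.

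**Step 2: compare with SAP 2.3.3.** The last two conditions in the table are exactly the ones that 2.3.3 states and the footnote omits. Without the study-drug exclusion, the literal words would also catch study caspofungin or fluconazole, which cannot be meant. The rule therefore cannot be run without limits that it does not state.

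**Step 3: size.** Let f be the share of mITT subjects with a pre-study antifungal for a listed indication. The documents do not give f, so 10% to 80% is assumed. Further assumptions are that f is equal in the two arms and that true eradication does not depend on prior treatment. Then:

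- derived rate = true rate × (1 − f)
- derived difference = true difference × (1 − f)

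For illustration, take a true rate of 70% (the plan's global-cure figure, not an eradication figure) and a true difference of −20 points:

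| f | Derived rate | Derived difference |
|---|---|---|
| 10% | 0.70 × 0.90 = 63% | −18 points |
| 25% | 0.70 × 0.75 = 52.5% | −15 points |
| 50% | 0.70 × 0.50 = 35% | −10 points |
| 80% | 0.70 × 0.20 = 14% | −4 points |

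If f differs between arms, say 55% against 45% with no true difference, the artificial difference is 0.70 × (0.45 − 0.55) = −7 points.

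**The case against.** The strongest reply is that the footnote should be read with the term it defines. A change of therapy is a change from study drug: Protocol 6.1.3 uses the phrase for clinical failures who need different treatment. Neighbouring rules point the same way. Table 2-1 and SAP 2.2.3 speak of rescue, and Table 2-4 of new systemic therapy. Data set specifications are still to be written from the SAP (SAP 1.1.1), and a sensible programmer would supply the limit. This stands as evidence of intent. It does not repair the text, because the footnote replaces the clinical phrase with a receipt-and-date rule, and a prespecified derivation should not rely on unstated limits.

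Two stronger inferences are not supported:

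- A reader might infer that prior-treated subjects are in fact being programmed as failures. No program or specification is shown, so only the consequence of applying the words as written can be stated.
- A reader might infer that the non-inferiority conclusions are biased. ACM does not use mycological response. The EMA primary uses the blinded DRC's determination (SAP 2.1 and 2.2.1). Table 2-2 does make mycological failure a global failure, but nothing says the DRC must take over the programmed value, and SAP 2.6 refers to mycological response as assessed by the DRC. The secondary confidence intervals are descriptive only (SAP 4.3.2).

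It is also fair that not every prior antifungal is caught. The subset in SAP 4.3.4 concerns any prior systemic antifungal, while the footnote needs a listed indication. The documents do not say how the indication for empiric treatment is coded.

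**Conclusion.** The defect is real and lies in the wording. Applied as written, the footnote makes subjects with permitted pre-study treatment for candidemia or invasive candidiasis derived mycological failures at all five visits, contrary to its evident purpose and to SAP 2.3.3. The direct damage is limited to derived eradication and the descriptive analyses that use it. The EMA primary is exposed only if the DRC adopts the derived response, and ACM is not affected.

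The size cannot be stated from the documents, because f is unknown. Under the assumptions above, rates and differences shrink by the factor 1 − f. The 10% to 80% range, the 70% rate and the 20-point difference are illustrations, not estimates. The 7-point artefact needs a 10-point imbalance in prior treatment, which under randomization could arise only by chance.

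**What to change.** Reword the triple-asterisk footnote so that a change of therapy means an antifungal that:

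- is not study drug;
- has one of the listed indications; and
- has a start date and time no earlier than the first study-drug dose and no later than the assessment day.

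Keep the EOT (+1 day) clause as it is, and apply the same definition to the matching condition in the Eradication row.

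Two cases need a sentence each, or the new limit could miss rescue therapy:

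- **Continued antifungals.** State how one begun before the first dose and carried on after it is classified. SAP 4.2.2 treats such a drug as concomitant, and Protocol 8.5 does not allow other systemic antifungals alongside study drug without discussion, unless the subject is a treatment failure.
- **Undatable antifungals.** SAP Appendix 8 assumes that an antifungal whose start cannot be placed preceded the first dose, unless its indication shows otherwise. State whether that assumption governs this endpoint.

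The cost is one footnote, two classification rules and the matching lines of the derivation program. No new data are needed, and the sample size and stated power do not change. The change belongs in a SAP amendment before database lock. If lock has passed, SAP 1.1.1 requires the change to be described in the clinical study report.
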